3.2 Primary Study Endpoints

- 1) Safety measured by occurrence of adverse events.
- 2) Pathological tumor response (pTR) in the primary tumor following surgical resection.

3.3 Secondary Study Endpoints

2-year locoregional control rates, progression-free survival, metastasis-free survival, and overall survival.

4 Subject Selection and Withdrawal

4.1 Inclusion Criteria

- 4.1.1 Patients ≥ 18 years old.**

- 4.1.2** Histologically confirmed diagnosis of squamous cell carcinoma of the oropharynx or neck.
- 4.1.3** Clinical T1, T2, T3, or T4 stage disease of the oropharynx (per AJCC 8th Ed).
- 4.1.4** Any clinical N stage disease (per AJCC 8th Ed).
- 4.1.5** Patients must be undergoing direct laryngoscopy +/- biopsy at the University of Pennsylvania as part of their work-up for consideration of definitive TORS and selective neck dissection.
- 4.1.6** Patients must sign an informed consent document that indicates they are aware of the investigational nature of the treatment in this protocol as well as the potential risks and benefits.
- 4.1.7** Ability to understand and the willingness to provide written informed consent.

4.2 Exclusion Criteria

- 4.2.1** Prior external beam radiation therapy to the head and neck.
- 4.2.2** Prior chemotherapy for head and neck cancer.
- 4.2.3** Tumor invades lateral pterygoid muscle, pterygoid plates, lateral nasopharynx, or skull base or encases carotid artery (i.e. AJCC 7th Ed. T4b for OPSCC).
- 4.2.4** Presence of distant metastatic disease.
- 4.2.5** Uncontrolled inter-current illness including, but not limited to, symptomatic congestive heart failure, unstable angina pectoris, connective tissue disease or psychiatric illness/social situations that would limit compliance with study requirements.
- 4.2.6** Known history of hypersensitivity to lidocaine or other amide local anesthetics.
- 4.2.7** Pregnant or breastfeeding.

4.3 Patient Selection and Inclusion

OPSCC is now the most common head and neck cancer diagnosed in the United States

with most cases attributed to HPV. HPV associated OPSCC is most frequently seen in middle-aged, white males (not Hispanic or Latino). We expect to have similar eligibility and enrollment demographics as other published trials on HPV associated OPSCC. For reference, RTOG 1016, which compared radiotherapy with cetuximab vs cisplatin, is the largest published randomized trial of HPV associated OPSCC in the United States with the following study demographics:⁸⁰

	IMRT + Cisplatin (n=406)	IMRT + Cetuximab (n=399)	Total (n=805)
Age (years)			
≤ 65	344 (85%)	345 (86%)	689 (86%)
> 65	62 (15%)	54 (14%)	116 (14%)
Mean (standard deviation)	57.7 (8.1)	57.4 (7.8)	57.6 (8.0)
Median (1 st - 3 rd quartile)	58 (52-63)	58 (52-63)	58 (52-63)
Min - max	33 - 83	33 - 80	33 - 83
Gender			
Male	373 (92%)	355 (89%)	728 (90%)
Female	33 (8%)	44 (11%)	77 (10%)
Race			
White	380 (94%)	367 (92%)	747 (93%)
Black or African American	17 (4%)	19 (5%)	36 (4%)
Other	2 (<1%)	8 (2%)	10 (1%)
Unknown	7 (2%)	5 (1%)	12 (1%)
Ethnicity			
Hispanic or Latino	11 (3%)	15 (4%)	26 (3%)
Not Hispanic or Latino	383 (94%)	369 (92%)	752 (93%)
Unknown	12 (3%)	15 (4%)	27 (3%)

4.4 *Subject Recruitment and Screening*

Subjects will be recruited from the practices of Otorhinolaryngology and Radiation Oncology at the University of Pennsylvania. The study CRC will verify eligibility using the criteria outlined in Section 4.1 and 4.2. Patients will be consented either in clinic or in the hospital.

4.5 *Clinical Evaluation and Staging Criteria*

- History and physical examination:
 - Primary tumor extent will be documented by the head and neck surgeon, with a particular focus on the degree (if any) of involvement of the soft palate and/or base of tongue.
- Laboratory studies:
 - HPV status will be determined based on p16-positivity by immunohistochemistry or HPV-positivity by in-situ hybridization.
 - Research blood tests will be drawn 1) prior to direct laryngoscopy/study intervention and 2) after the direct laryngoscopy/study intervention (but before definitive treatment).
- Pathologic evaluation
 - In addition to standard pathologic evaluation of biopsy and surgical

specimens, pTR will be calculated and categorized as pTR-0 ($\leq 10\%$), pTR-1 ($\leq 10-49\%$), and pTR-2 ($\geq 50\%$) by the designated study pathologist ([name], PhD).

- Staging imaging studies will be dictated by standard of care.
- Eligibility for this study will be according to AJCC 7th and 8th Edition staging. AJCC 7th Edition staging data will be collected and recorded in the electronic medical record (Epic) for all patients as this staging is currently being used clinically to determine indications for adjuvant radiotherapy.

4.6 Off-Study Criteria

- Extraordinary Medical Circumstances: If at any time the constraints of this protocol are detrimental to the subject's health, the subject will be removed from protocol therapy. In this event, the reasons for withdrawal will be documented if possible.
- Subject's refusal to continue treatment or decision for non-surgical treatment: In this event, the reasons for withdrawal or decision for non-surgical treatment will be documented if possible.
- Patients may be taken off study at any time at the discretion of the Principal Investigator.

4.7 Study Duration

With an estimated accrual of 1-2 patients per month, it is anticipated that accrual will continue for approximately 2-years. The anticipated accrual rate is based on accrual to our prior TORS trial protocols. We find that most of our patients with HPV associated OPSCC are highly motivated to enroll on clinical trials, as they are often referred to Penn Medicine specifically for that reason.

5 Study Procedures

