Number of Subjects	30 evaluable subjects
Diagnosis and Main Inclusion Criteria	
 - ≥18 years old with OPSCC undergoing direct laryngoscopy for consideration of TORS and neck dissection.
Study Regimen	
 - Patients will be randomized and blinded to intratumoral injection of 1% lidocaine (intervention arm) or no injection (control arm) at the time of direct laryngoscopy and biopsy prior to TORS and neck dissection. 
 o Intervention arm: While under general anesthesia after direct laryngoscopy with biopsy, 1% lidocaine will be injected under direct visualization (not exceeding the maximum tolerated dose of 4.5 mg/kg body weight) into the primary tumor with the aim to distribute the lidocaine evenly into the tumor. o Control arm: Direct laryngoscopy with biopsy with no injection. - Blood samples will be obtained before and after direct laryngoscopy/study intervention. - Pathologic tumor response (pTR) will be determined from surgical specimens.

Statistical Methodology	
This is a patient-blinded, randomized phase I study assessing safety, pathologic treatment effects, and oncologic outcomes from intratumoral lidocaine injection vs no injection at the time of direct laryngoscopy prior to TORS and neck dissection for HPV associated OPSCC. The total sample size is estimated to be 30 patients total (split approximately equally between the two groups). The proportion of patients with a pathologic tumor response (pTR) $\geq 50\%$ (pTR-2) in the primary tumor following surgical resection will be compared between intervention and control arms using a one-sided Fisher's exact test with a significance level of 0.05. The 2-year locoregional control (LRC) rates, progression-free survival (PFS), metastasis-free survival (MFS), and overall survival (OS) will be estimated using the Kaplan–Meier method and compared using log-rank test between the two arms.

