-------------------------	-------------------------------------------------------------------------------------------------------------------------------------------------------------------------------------------------------------------------------------------------------------------------------------------------------------------------------------------------------------------------------------------------------------------------------------------------------------------------------------------------------------------------------------------------------------------------------------------------------------------------------------------------------------------------------------------------------------------------------------------------------------------------------------------------------------------------------------------------------------------------------------------------------------------------------------------

Study Schema

Primary endpoints: 1) safety, 2) proportion of patients with pTR-2

Secondary endpoints: 2-year LRC, MFS, PFS, OS

* Denotes trial-related (i.e., not institutional standard of care)

1 Introduction

Based on evidence that lidocaine may activate apoptosis in cancer cells and/or limit metastasis, this randomized phase I study will establish the safety and efficacy of intratumoral lidocaine injection at the time of direct laryngoscopy prior to TransOral Robotic Surgery (TORS) and neck dissection for oropharyngeal squamous cell carcinoma (OPSCC). The primary objective of the study is to determine if intratumoral lidocaine injection is safe and causes a major pathologic treatment effect in the primary tumor following surgical resection. The secondary objectives will be to determine if intratumoral lidocaine injection improves locoregional control (LRC) rates, progression-free survival (PFS), metastasis-free survival (MFS), and overall survival (OS) compared to no injection (standard of care).

Background

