3.1 General Design

This is a phase I patient-blinded, randomized controlled trial evaluating intratumoral lidocaine injection prior to definitive surgery in HPV associated OPSCC. Patients with OPSCC undergoing direct laryngoscopy who are being considered for definitive TORS

and selective neck dissection, will be eligible. Patients will be randomized and blinded to intratumoral injection of 1% lidocaine (intervention arm) or no injection (control arm) at the time of direct laryngoscopy. After administration of general anesthesia and biopsy, lidocaine will be injected under direct visualization (not exceeding the maximum tolerated dose of 4.5 mg/kg body weight) into the primary tumor. The control arm will receive no injection.

Blood samples will be obtained prior to direct laryngoscopy/study intervention (pre-biopsy) and again after the intervention (post-biopsy). The pTR rate (defined above and in published literature^{78, 79}) will be determined by the designated study pathologist ([name], PhD) with head and neck expertise using increments of 10% for the biopsy and surgery specimens. The scores will be grouped as pTR-0 (<10%), pTR-1 (10%–49%), and pTR-2 (≥50%).

Patients will otherwise receive institutional standard of care treatment including TORS primary site resection, selective neck dissection, and additional indicated adjuvant radiation therapy with or without chemotherapy. All enrolled patients will be assessed for safety measured by adverse events. If a patient does not ultimately receive primary surgery following their direct laryngoscopy/study intervention (based on surgical candidacy, patient preference, or other reasons), then they will not be counted as an evaluable subject, as the primary endpoint pTR requires a surgical specimen for evaluation. If a patient is determined to have a pathology other than HPV associated OPSCC after their direct laryngoscopy, then they will not be counted as an evaluable subject.

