5.1 General study design

Patients will be enrolled to reach 30 evaluable subjects on this phase I patient-blinded, randomized controlled trial investigating the feasibility and safety of intratumoral 1% lidocaine injection at the time of direct laryngoscopy prior to definitive surgery in HPV associated OPSCC patients. Patients with a clinically apparent primary tumor (i.e. clinical T1-T4), any clinical N stage, and M0 disease (per AJCC 8th Edition) undergoing direct laryngoscopy who are being considered for definitive TORS and selective neck dissection, will be eligible. Patients will be blinded to the intervention which will be administered as dictated by the protocol, according to Section 3.1 above. Randomization will be performed using the “Clinical Trial Randomization Tool” from The National Cancer Institute's Division of Cancer Prevention.⁸¹

Clinical evaluations will be performed according to routine clinical care, which is left to the discretion of the treating physician. This will include a baseline evaluation prior to direct laryngoscopy/study intervention.

All patients will be asked to take a short survey about pain (2 questions) at their follow up appointment after their direct laryngoscopy and biopsy.

Locoregional recurrence will be defined as biopsy-proven recurrent squamous cell carcinoma at the original, primary tumor site, or in the neck.

5.2 *Surgery*

Surgery will be performed per standard of care consisting of TORS primary site resection, selective neck dissection, and external carotid artery vessel ligation. The decision to stage the neck dissection and TORS will be determined at the discretion of the head and neck surgeon. Intraoperative continuous monitoring of circulation and respiration will be performed.

5.3 *Radiation Therapy*

Patients who have indications post-operative radiation therapy per NCCN guidelines⁵ will be referred to a radiation oncologist who specializes in the treatment of head and neck cancer within the University of Pennsylvania Health System, with the decision on whether to treat with radiation therapy determined at the discretion of the consulting radiation oncologist.

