An outline of the typical study visit schedule is provided below. There will be no planned additional study visits compared to routine, standard of care (SOC). Clinical research procedures are underlined in the table for clarification purposes.

Visit Number	Visit Procedures
Visit 1	Come to the clinic for a routine (SOC) clinic visit(s). Decide if you want to participate in the study, ask questions, sign the consent form if you do want to participate.
Visit 2	Have a pre-operative research blood draw with blood sample storage on the day of your direct laryngoscopy with biopsy.

	
Study Intervention: Participants will be randomly assigned to two groups.
 
 • Group 1 (Intervention Arm) – Biopsy and injection of lidocaine into tumor while you are under general anesthesia for your direct laryngoscopy. • Group 2 (Control Arm) – Biopsy without injection of lidocaine while you are under general anesthesia for your direct laryngoscopy.
Visit 3	Routine (SOC) clinic visit to discuss the results of your direct laryngoscopy with biopsy and have a research study blood draw with blood sample storage . You will also be asked to take a short survey.
Visit 4	Routine (SOC) treatment with primary surgery or primary radiation with storage of tumor tissue for research . This will allow researchers to study leftover tissue removed during your routine care.
Visit 5	Routine (SOC) follow up for cancer surveillance per National Comprehensive Cancer Network guidelines.

6 Statistical Plan

This study is considered exploratory because, to our knowledge, no prior published data exists on the effects of lidocaine injection on pathologic tumor response, survival, and recurrence in HPV associated OPSCC. The planned sample size for this phase I trial is 30 evaluable subjects split equally between the intervention and control arms. Subjects will need to have a definitive diagnosis of HPV associated OPSCC and undergo surgery (TORS and neck dissection) to be considered evaluable.

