The co-primary objectives of this study are to determine safety and if the proportion of patients with pTR-2 in the primary tumor is different in the intervention group compared to the control arm. All enrolled participants, regardless of HPV status or final pathology, will be included in the primary safety analysis. Thus, any adverse events or dose-limiting toxicities observed in participants will contribute to the overall safety assessment of intratumoral lidocaine.

For the pathologic response primary endpoint, H_0 is that there is no difference in the proportions of patients with pTR-2 between the intervention or no intervention (control) groups; H_a is that the intervention arm is associated with a higher proportion of pTR-2. The proportion of pTR-2 will be compared between the intervention and control arms using a one-sided Fisher's exact test with a significance level of 0.05. A 95% confidence interval will be used. We estimate that a sample size of 30 patients is needed to allow us to detect

with 80% power at the one-sided alpha level of 0.05 a major pathologic treatment rate of 30% in the intervention arm compared to 0% in the control arm.

In addition to hypothesis testing for the pathologic response primary outcome, we will use within-between interaction models to account for the effects of the treatment and the interaction between treatment and patient and disease factors including age, sex, disease stage, and adverse pathologic features (e.g. tumor grade, perineural invasion, lymphovascular invasion). We will estimate means and standard deviations for each group and the correlation within subjects to better understand the relationship between repeated measures. We will use mixed-effects models to handle within-subject correlations and between-subject comparisons.

The secondary endpoints include 2-year locoregional control (LCR) rates, progression-free survival (PFS), metastasis-free survival (MFS), and overall survival (OS). PFS will be defined as time from random assignment to disease progression or death from any cause. MFS will be defined as time from random assignment to first evidence of distant metastatic disease or death from any cause. OS will be defined as the time from random assignment and death due to any cause. 95% confidence intervals will be used. LRC rates, PFS, MFS, and OS will be estimated using the Kaplan–Meier method, and log-rank test will be used to compare the two groups using a significance level of 0.05.

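### The stated study duration of 2 years equals the accrual period, leaving no room for the 2-year secondary endpoints and no stated follow-up after the last patient

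*Protocol*

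**What the plan says.** The Study Summary table gives Study Duration as 2 years. Section 4.7, under the same heading, expects 1-2 patients per month and says "it is anticipated that accrual will continue for approximately 2-years". It mentions nothing after accrual.

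The schema lists "Secondary endpoints: 2-year LRC, MFS, PFS, OS". Section 3.3 names "2-year locoregional control rates, progression-free survival, metastasis-free survival, and overall survival", and the Statistical Methodology row of the Summary says "The 2-year locoregional control (LRC) rates, progression-free survival (PFS), metastasis-free survival (MFS), and overall survival (OS) will be estimated" by Kaplan-Meier. Section 6 starts the clock for progression-free, metastasis-free and overall survival at randomization; for example, "OS will be defined as the time from random assignment and death due to any cause". It adds log-rank comparisons at the 0.05 level.

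On follow-up, the last row of the visit table in Section 5.7 (Visit 5) says "Routine (SOC) follow up for cancer surveillance per National Comprehensive Cancer Network guidelines", with no length or end. On numbers, Section 5.1 says "Patients will be enrolled to reach 30 evaluable subjects". Under Section 3.1, a patient who does not go on to primary surgery is not evaluable ("then they will not be counted as an evaluable subject, as the primary endpoint pTR requires a surgical specimen for evaluation"), nor is one whose tumor proves not to be HPV-associated.

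**The concern.** A 2-year endpoint timed from each patient's own randomization needs 24 months of observation after the last patient enters. A study that lasts 2 years and spends about 2 years accruing cannot supply that. The 2-year figure can be read in two ways, and both need correcting:

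- **Total duration.** The four secondary endpoints cannot be estimated at 24 months, because almost every patient is censored earlier.
- **Accrual only.** The Summary entry is mislabelled, the study is about twice as long as stated, and the protocol never says how long patients are followed.

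The stake is the whole set of secondary endpoints. The two primary endpoints, safety and pathologic tumor response, do not depend on long follow-up.

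**Working it through.** **Inputs.** Accrual of 1-2 patients per month (Section 4.7); 30 evaluable patients (Section 5.1); endpoint horizon of 24 months (schema, Section 3.3); time origin at randomization (Section 6); stated duration of 24 months (Study Summary). Entry is taken as even over the accrual period, which is an assumption.

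**Step 1: the plan's own figure.** Accrual time is A = N / rate. For N = 30, A = 30/1 = 30, 30/1.25 = 24, 30/1.5 = 20 and 30/2 = 15 months. The stated accrual of about 2 years corresponds to 1.25 per month and lies inside the stated range.

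**Step 2: follow-up if the study closes at month 24.** A patient entering at month t has 24 - t months of follow-up. With A capped at 24, median follow-up = 24 - A/2. The number with at least 12 months is 12 × rate, and with at least 18 months 6 × rate.

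**Step 3: length needed.** Total = A + 24, using the uncapped A.

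| Rate per month | A for 30 (months) | Enrolled by month 24 | Median follow-up (months) | At least 12 months | At least 18 months | A + 24 (months) |
|---|---|---|---|---|---|---|
| 1 | 30 | 24 | 24 - 24/2 = 12 | 12 | 6 | 54 |
| 1.25 | 24 | 30 | 24 - 24/2 = 12 | 15 | 7.5 | 48 |
| 1.5 | 20 | 30 | 24 - 20/2 = 14 | 18 | 9 | 44 |
| 2 | 15 | 30 | 24 - 15/2 = 16.5 | 24 | 12 | 39 |

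At every rate, only a patient randomized at time zero reaches 24 months. Placing patients one at a time at equal intervals, instead of using the continuous formula, changes these figures very little: at 2 per month the median is 16.75 months, 25 patients have at least 12 months, and one has 24.

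**Step 4: non-evaluable patients.** The target is 30 evaluable, so more are enrolled if any are non-evaluable. The protocol gives no rate. Assuming 10-20%:

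- N = 30/0.9 = 33.3 (34) to 30/0.8 = 37.5 (38).
- A = 34/2 = 17 to 38/1 = 38 months.
- Total = 17 + 24 = 41 to 38 + 24 = 62 months.
- Median follow-up at month 24 runs from 12 months (1 per month) to 24 - 17/2 = 15.5 months (2 per month, 34 enrolled).

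**Step 5: search for a follow-up period elsewhere.** Visit 5 has no length. The only follow-up window with a stated length is 30 days after injection, for adverse events (Section 7.1). The audits in Section 9.2 run only while the trial is open to accrual. None of these sets a follow-up length per patient, a minimum after the last patient, or an end of study.

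**The case against.** The strongest reply is that 2 years was meant as accrual. Section 4.7 discusses nothing else, the Summary probably repeats its figure, and nothing says that data collection stops at month 24. Visit 5 is open-ended, and a 2-year endpoint itself implies 24 months per patient. On that reading no estimate is lost. This reading is plausible, and the follow-up figures in the table apply only to the other one. But it leaves a Summary entry that is wrong by about half and a follow-up length that has to be inferred.

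Other points carry partial weight:

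- The study is declared exploratory, and the Background cites locoregional control above 95% and 3-year survival near 90%. Few events are expected even with full follow-up. That limits the consequence but does not reconcile the durations.
- Kaplan-Meier and log-rank methods accommodate censoring, so a log-rank comparison would lose information without becoming invalid. A 24-month estimate with about one patient at risk would still be unusable.
- In Section 3.3 the 2-year qualifier could be read as applying to locoregional control alone. The schema attaches it to the whole list, and a single 2-year endpoint would still need 24 months per patient.
- Consent pages and the schema graphic are not available, and an analysis plan may fix the data cut-off. None of these would correct the duration stated in the Summary.
- The longest totals use 1 patient per month, slower than 2 years of accrual implies. With accrual of 24 months the total is 48.

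**Conclusion.** The concern holds. As written, a 2-year study with about 2 years of accrual cannot produce its 2-year secondary estimates at any accrual rate in the stated range. This conclusion does not depend on the assumed non-evaluable rate; even entry affects the medians and counts but not the shortfall. On the accrual-only reading the defect is smaller but remains: the duration is stated as 24 months against about 48 needed, and follow-up is unstated. This should be fixed. It does not threaten the primary endpoints.

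**What to change.** In the Study Summary and Section 4.7, state the duration as accrual of about 2 years plus 24 months of follow-up after the last randomization, about 4 years in total. The range is 39-54 months if 30 patients are enrolled at 1-2 per month, and longer if some enrolled patients are not evaluable. State that 2-year locoregional control, progression-free, metastasis-free and overall survival are estimated once that follow-up is complete.

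The cost is two short wording changes, submitted to the IRB as an amendment (Section 10). The stated study becomes longer and the secondary results come later. No visits are added, because the data come from the routine surveillance already listed as Visit 5.
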